6.1.3 Route of Administration

Study drugs are applied topically to surgical bed prior to closure of skin.

7 Study Procedures and Schedule

7.1 Study Procedures/Evaluations

7.1.1 Study Specific Procedures

Patients meeting inclusion criteria will be randomized at their preoperative appointments with a sealed envelope method and an initial evaluation will be completed for pre-operative pain levels using the numerical pain rating scale. At the conclusion of their respective surgery just prior to wound closure, the appropriate medications will be topically administered into the wound and the wound will be closed via standard method. Patients will record pain scores at home daily and also record the amount of pain pills (Norco 5/325mg) needed postoperatively until post operative day 14.

Preoperative analog pain scoring will be performed followed by postoperative analog pain scoring on postoperative day 0-14. Compliance will be recorded by the patient in a written form. Number of opioid pain medications taken will also be recorded by patient in a written form.

Analog pain scoring preoperatively on day of surgery and postoperatively day of surgery. Pain scale from 0 (no pain) to 10 (highest level of pain ever experienced). This scoring system will also be utilized by the patient daily until postoperative day 14.

Opioid prescriptions (Norco 5/325 mg) will be given to patients post operatively. Total number of pills taken up until post operative day 14 will be recorded by the patient.

This will allow us to track the patients relative pain pre and postoperatively until postoperative day 14.

- Medical history will be obtained in hand surgery clinic at initial patient presentation.

CONFIDENTIAL

This material is the property of the NYU School of Medicine and Langone Medical Center. Do not disclose or use except as authorized in writing by the study sponsor
Interventional Template Version: 11 January 2019

- Medication history will include details about the specifics of their hand problem along with a past medical history that includes history of chronic pain, narcotic addiction, recreational drug dependency, psychiatric pathologies, allergy to drugs and preferences for anesthesia. Those patients who only wish to have an anesthetic upper extremity block performed by anesthesia will not qualify for the study.
- Physical examination will consist of a full hand examination. The most important criteria will be the presence or absence of an already open wound prior to surgical intervention.
- The patients will be counseled on the study objectives and methods of data collection. The numerical pain rating scale will be explained in detail to the patient.
- The patients will be administered a pain diary in which they will be able to log their daily pain level at the same time each day (AM) based on the numeric pain scale (1-10). They will also be instructed to log their pain medication usage and the number of pills of Norco 5/325 mg that are consumed. This log will continue daily for a total of 14 days postoperatively.

The first visit will be the initial evaluation of the patient when they present for their individual hand surgery evaluation. If they qualify for their study, an initial preoperative pain scale will be used to assess their pain level.

The next assessment will be on the day of surgery. The patient will be evaluated in the preoperative holding area and another pain level evaluation will be done for a POD#0 timepoint.

The patient will be evaluated in PACU for total time in PACU.

Each patient will receive their log book and take it home with them. The patients will be called on each day by the study team to ensure that they have been logging their daily pain score. The study team will call the patient for this purpose.

The patients will be seen in person on their first postoperative visit (approximately 1-2 weeks later). If this is prior to postoperative day 14, they will follow up again in hand clinic after day 14 (in 4-6 weeks post-surgery) to submit their log books.

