5.5 Duration of Study Participation

Pre-operative visit will occur up to 3 months prior to surgery. Final Study visit will occur up to 6 weeks after surgery. Primary endpoint (returning completed pain diary to study staff) occurs at Day 14. Participants

CONFIDENTIAL

This material is the property of the NYU School of Medicine and Langone Medical Center. Do not disclose or use except as authorized in writing by the study sponsor
Interventional Template Version: 11 January 2019

remain enrolled in the study up until their standard of care post-op visit, which typically occurs 4-6 weeks after surgery. Participation is complete when participants complete their final standard of care post-op visit.

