5.6 Total Number of Participants and Sites

Patients will be recruited from NYU Langone Health and from Bellevue Hospital Center.

Recruitment will end when approximately 40 participants are enrolled. It is expected that approximately 40 participants will be enrolled in order to produce 40 evaluable participants.

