5.7 Participant Withdrawal or Termination

5.7.1 Reasons for Withdrawal or Termination

Participants are free to withdraw from participation in the study at any time upon request. An investigator may terminate participation in the study if:

- Any clinical adverse event (AE), laboratory abnormality, or other medical condition or situation occurs such that continued participation in the study would not be in the best interest of the participant
- The participant meets an exclusion criterion (either newly developed or not previously recognized) that precludes further study participation

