6.1.1 Acquisition

All drugs in this study are readily available at the hospitals where the study is to be performed. Nursing staff will verify expiration date and untampered vials prior to use intraoperatively. Unused drugs will be disposed of by all proper protocols per the hospital.

CONFIDENTIAL

This material is the property of the NYU School of Medicine and Langone Medical Center. Do not disclose or use except as authorized in writing by the study sponsor
Interventional Template Version: 11 January 2019

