7.2 Study Schedule

Screening/Baseline Visit (up to 3 months prior to day of surgery)

- Obtain informed consent of potential participant verified by signature on written informed consent for screening form.
- Review medical history to determine eligibility based on inclusion/exclusion criteria.
- Review medications history to determine eligibility based on inclusion/exclusion criteria.
- Perform medical examinations needed to determine eligibility based on inclusion/exclusion criteria.
- Schedule day of surgery where primary intervention will be performed.
- Provide participants with information regarding tranexamic acid, and operative steps for administration of drugs into surgical wound prior to closure.
- Provide participants with log books.
- Randomize patient using sealed envelope method.

Day of Surgery

- Verify patient still meets inclusion/exclusion criteria.
- Administer study treatment
- Patient fills out Day 1 of pain diary

Intermediate Visits

- Participants will be called via phone each day by the study team to ensure they have completed their daily log of numerical pain rating scale and number of pain pills taken.
- They will arrive for an intermediate visit on their first postoperative visit (variable time, between 3-14 days postoperatively). Log books will be collected only after postoperative day 14.

Final Study Visit (up to 6 weeks post surgery)

CONFIDENTIAL

This material is the property of the NYU School of Medicine and Langone Medical Center. Do not disclose or use except as authorized in writing by the study sponsor
Interventional Template Version: 11 January 2019

Pain logs will be collected from participants who have not already returned them to study staff. The participants will be released of their duties to the study once the log books have been returned to the physicians. They will continue their routine follow up per the follow up schedule for each hand surgery procedure. No additional data is collected for study purposes at post-op visits beyond data collected per standard of care.

8 Assessment of Safety

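### Patients are randomised up to 3 months before the only study treatment and before the final eligibility check, with no stated concealment and no rule for those never treated

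*Combined protocol and SAP*

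**What the plan says.** - **Time of allocation.** Section 7.1.1: "Patients meeting inclusion criteria will be randomized at their preoperative appointments with a sealed envelope method". Section 4.1 agrees. In section 7.2 and the Schematic of Study Design, "Randomize patient using sealed envelope method" is the last item of the screening/baseline visit.
- **Gap to treatment.** Section 5.5: "Pre-operative visit will occur up to 3 months prior to surgery". Three months is the maximum. Section 13.3.2 allows consent as late as the day before surgery, so some gaps will be short.
- **Treatment.** One topical application at the end of the operation, before the skin is closed (6.1.3, 7.1.1).
- **Check after allocation.** The first day-of-surgery item in section 7.2 is "Verify patient still meets inclusion/exclusion criteria". Section 5.7.1 lets an investigator end participation if "The participant meets an exclusion criterion (either newly developed or not previously recognized) that precludes further study participation".
- **Counting.** Section 5.4 recruits until 10 patients per group have been randomised, not treated. Section 5.6: "It is expected that approximately 40 participants will be enrolled in order to produce 40 evaluable participants".
- **Analysis.** Section 10.1.2 removes any patient with missing diary data.
- **Drug supply.** Section 6.1.1: "All drugs in this study are readily available at the hospitals where the study is to be performed".

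The documents do not say who opens the envelope, when it is opened, or which party the single blind covers. They give no rule for patients randomised but not treated, no replacement rule and no loss allowance.

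**The concern.** Between the pre-operative visit and wound closure, a randomised patient can cancel or postpone surgery, develop an open wound, or end up with a supra/infraclavicular block (exclusion 7). Each of these happens after the arm is fixed. Two things are at stake.

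The first is selection. The plan schedules an eligibility decision after allocation and does not require the person making it to be unaware of the arm. If knowledge of the arm influenced who was excluded, the groups analysed would no longer be the groups randomised.

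The second is numbers. A patient who is never treated says nothing about an intervention given only in theatre, has no postoperative diary, and is dropped under section 10.1.2, but has already used one of the 40 places.

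No stated purpose requires the arm to be known so early. The drugs are held at the hospitals, they are not used until closure, and no pre-operative step in section 7.2 depends on the allocation.

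**Working it through.** **1. Order of events, from sections 7.1.1, 7.2 and 6.1.2.** Consent and screening; randomisation; a gap of up to 3 months; eligibility re-check and a further pre-operative pain score in the holding area; anesthetic and the surgeon's local block before incision; operation; study mixture; closure. The re-check, the holding-area pain score, the anesthetic and the block all follow allocation.

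**2. The plan's own figure.** With a proportion d of randomised patients lost, evaluable = 40 × (1 − d). Setting this equal to 40 gives d = 0. The figure in section 5.6 is therefore reproduced only with zero loss. The 10 per arm cannot be checked, because section 10.1.1 gives no effect size, standard deviation, power or dropout rate.

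**3. Size under assumed loss.** The documents state no rate, so d below is an assumption. It covers only the interval between allocation and treatment.

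| Assumed d | Treated, 40 × (1 − d) | Average per arm | Randomised to treat 40, 40/(1 − d) rounded up |
|---|---|---|---|
| 5% | 38 | 9.5 | 43 |
| 10% | 36 | 9.0 | 45 |
| 15% | 34 | 8.5 | 48 |

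If losses are independent, the chance that none occurs is (1 − d)^40: 12.9%, 1.5% and 0.15%. For an even chance of no loss, d can be at most 1 − 0.5^(1/40) = 1.7%.

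**4. Cost in precision.** For a difference between two equal arms, the standard error grows by √(10/n). At n = 9.5, 9.0 and 8.5 this is 1.026, 1.054 and 1.085, so the standard error is about 3%, 5% or 8% larger. The cost is real but modest.

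**5. Selection.** In an arm of 10, one removal influenced by the allocation is 1/10 = 10% of that arm. How likely such a removal is cannot be computed from the documents. The text contains no safeguard against it.

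**The case against.** The strongest reply has four parts.

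*Anesthesia is screened in advance.* A reader might infer that exclusion 7 is settled only in theatre. Section 7.1.1 takes anesthesia preference in the screening history and rules out patients who want only an upper-extremity block, and every arm receives a surgeon's local block. This stands: late failures on exclusion 7 are reduced. They are not removed, because the criterion turns on the block actually received.

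*Biased re-selection is conjecture.* This stands in part. The documents do not exclude an envelope assigned at the visit and opened only in theatre, and section 5.7.1 does not itself say that a terminated patient leaves the analysis. Cancellations unrelated to arm cost numbers without biasing the comparison. What remains is that neither concealment until treatment nor a blinded re-check is specified.

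*The shortfall is assumed.* A reader might infer that 40 enrolled cannot yield 40 evaluable. The documents do not support that: no loss rate is given, section 5.6 speaks of about 40, and section 10.1.1 sets 40 as a minimum. More could be enrolled, although no rule says when. The small probabilities of zero loss would look poor for any trial of 40 and measure neither bias nor power.

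*Late consent.* A reader might also infer that a patient who consents the day before surgery has no visit left at which to be randomised. That is speculation, since a visit up to 3 months before surgery can fall on that day.

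**Conclusion.** The point holds as an inexpensive improvement to the design. Allocation comes before the final eligibility check and before treatment, by up to 3 months, with no stated need, no specified concealment until treatment and no rule for patients randomised but never treated. Such patients count toward recruitment and then drop out of the analysis, and an exclusion on the day of surgery could be made with the arm known.

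It should not be read as showing that selection has occurred or that the randomised comparison is broken. The size rests on assumed losses of 5% to 15%, which would leave 38 to 34 treated and raise the standard error of a pairwise comparison by about 3% to 8% with equal arms. The more important gain from the change is protection against arm-aware exclusion, which the documents do not allow anyone to quantify.

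**What to change.** Keep consent, screening and the baseline pain score at the pre-operative visit. Move the randomisation item to Day of Surgery in sections 4.1, 7.1.1 and 7.2 and in the schematic. State that the next sequentially numbered opaque envelope, from one series per site, is opened only after eligibility has been re-verified and the anesthetic and pre-incision block have been given, and early enough before closure to prepare the assigned mixture. State in sections 5.4 and 5.6 that the 40 are counted from that point. Cancellations and failed re-checks then happen before randomisation and cost no randomised patient, and the holding-area pain score also precedes allocation.

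The cost is a protocol amendment and modest theatre logistics: envelopes held at both sites, and the mixture, including thrombin supplied as a powder for reconstitution (2.2), prepared during the operation. No patients, visits or procedures are added.

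The change closes the interval between the visit and the operation. It does not address removal for incomplete diaries (10.1.2) or unequal arms under simple randomisation (10.1.1), which need their own remedies.

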4.2.2 Secondary Study Endpoints

Number of pain pills used

Total time in PACU

5 Study Enrollment and Withdrawal

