6.1.2 Dosing and Administration

Tranexemic acid:

We plan on using a total dose of 500 mg (20 mL) total for each case.

Aminocaproic acid: We will use a total of 1000 mg total for each case.

Recombinant Human Thrombin:

For our topical application, we will use a total of 10000 units per open surgical study arm involving use of Thrombin.

Lidocaine Hydrochloride with Epinephrine:

We plan on using a total of 5 mLs per open surgical study arm involving lidocaine hydrochloride and epinephrine.

Bupivacaine Hydrochloride with Epinephrine:

We plan on using a total of 5 mLs per open surgical study arm involving bupivacaine hydrochloride with epinephrine.

Each study arm will receive an intraoperative local block at the site of surgery by the operative surgeon prior to incision.

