10.1 Statistical and Analytical Plans (SAP)

10.1.1 General Approach

Each arm of this randomized, single-blinded, placebo-controlled study will have a minimum of 10 patients. There will be a minimum of 40 patients in the study. Patients will be randomized using Microsoft Excel.

Simple randomization will be used to determine the treatment arm. In order for us to power our study based on a previous similar study at NYU for topical application (Haddock et al., Thrombin and Topical Local Anesthetic for Postoperative Pain Management), we will need 10 patients for each individual treatment arm to detect any difference in the outcome.

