10.1.2 Analysis of the Primary Efficacy Endpoint(s)

Data will be expressed either as a mean (SD) or median and interquartile range (IQR). To evaluate PACU time as a function of each group, a one way analysis of variance test followed by a Tukey-Kramer post hoc test will be performed. To assess the number of pain pills need as a function of each group, a Kruskal-Wallis test followed by a Dunn post hoc analysis will be performed. To compare pain levels between the treatment arms, pain scores on a scale of 1 (lowest aka no pain) to 10 (highest pain experienced in life) will be collected daily via a patient log. They will be analyzed as a change from baseline (preoperative) pain levels and analyzed used a series of two proportion z tests with a family error rate equal to 0.05. For all tests, a P value of less than 0.05 will be considered statistically significant.

Pain is a subjective measure. We will be using an analog pain scale and reference them to the patients pre and postoperatively to account for this. Patients may take over the counter pain medication postoperatively. We cannot control the patient's use of over the counter pain medications while at home, thus we will have to rely on their accuracy and honesty for this study.

Patients will be called daily to ensure completion of daily log books. If they are not able to do this, they will be removed from the study analysis. If the patients return to clinic at 4-6 weeks post-surgery and they have completed their logs, their data will still be accepted. But if there is missing data, they will be removed from the analysis.

11 Source Documents and Access to Source Data/Documents

All data will be stored on HIPAA compliant and encrypted REDCap, approved by the institution and managed by MCIT.

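### PACU time is compared by ANOVA on arm alone although anesthesia beyond the surgeon's local block is not standardized; if it varies, precision is lost, and a planned-anesthesia term would recover it.

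*Combined protocol and SAP*

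**What the plan says.** Section 4.2.2 lists "Total time in PACU" as a secondary endpoint, and section 2.2.1 makes shorter PACU time one of the stated hypotheses. Section 7.1.1 covers its collection in one sentence: "The patient will be evaluated in PACU for total time in PACU".

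The analysis in section 10.1.2, repeated in the Protocol Summary, is "a one way analysis of variance test followed by a Tukey-Kramer post hoc test will be performed". No covariate or stratum is named. Section 10.1.2 adds: "For all tests, a P value of less than 0.05 will be considered statistically significant". Section 10.1.1 specifies simple randomization and gives the sample size as follows: "we will need 10 patients for each individual treatment arm to detect any difference in the outcome".

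On anesthesia, section 6.1.2 states: "Each study arm will receive an intraoperative local block at the site of surgery by the operative surgeon prior to incision". Section 5.1 admits any elective hand surgery. Section 5.2 excludes supraclavicular and infraclavicular blocks, and section 7.1.1 disqualifies patients who want only an upper-extremity block given by anesthesia. The history in section 7.1.1 includes "allergy to drugs and preferences for anesthesia". No section says whether general anesthesia, sedation or neither accompanies the surgeon's block, or that the type is entered as study data.

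**The concern.** PACU time can reflect recovery from general anesthesia or sedation as well as pain. Where patients have different types, the differences in stay that follow have nothing to do with the study solution. A model with arm as its only term treats them as noise.

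Two consequences follow. The residual variance rises, so a real difference between arms is harder to detect. And with 10 patients per arm and no stratification, the types can fall unevenly across arms, so that the observed arm means shift by chance in a single trial. Neither biases the comparison on average. At this sample size, though, there is little precision to spare on one of the trial's stated hypotheses.

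**Working it through.** **The plan's own figure.** The 10 per arm cannot be reproduced: no endpoint, effect size, SD or power is attached to it. It can be inverted. For a four-group F test with N = 40 and alpha 0.05, 80% power needs Cohen's f = 0.551. For a Tukey pairwise comparison, 80% power needs a difference of 1.59 SD. Only large effects on PACU time are detectable even in the ideal case.

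**Inputs from the documents.** Four arms of 10 (10.1.1, equal sizes taken as intended); alpha 0.05 and arm as the only term (10.1.2).

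**Assumed inputs (the documents give none).** SD of PACU time within an anesthesia type, 30 minutes; one arm shorter than the other three by 45 minutes; two anesthesia types with share p of one type; difference D minutes between types.

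**Step 1, no anesthesia effect.** Noncentrality for one arm differing from three:

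λ = n × (3/4) × (45/30)² = 10 × 0.75 × 2.25 = 16.875

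With 3 and 36 degrees of freedom, power is 92%.

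**Step 2, anesthesia mix left in the error term.** The residual variance is multiplied by v = 1 + p(1 − p)(D/30)², and λ is divided by v. With p = 0.5:

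| D (min) | v | λ/v | Power, arm only |
|---|---|---|---|
| 0 | 1.000 | 16.875 | 92% |
| 15 | 1.0625 | 15.88 | 90% |
| 30 | 1.250 | 13.50 | 84% |
| 45 | 1.5625 | 10.80 | 75% |
| 60 | 2.000 | 8.44 | 63% |

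Simulation of the same set-up gives about 84-85% at 30 minutes and 62-64% at 60.

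**Step 3, anesthesia type in the model.** The type effect leaves the residual. The cost is one degree of freedom and a small loss from chance overlap of type with arm: λ × (1 − 1/39) = 16.44 with 35 error degrees of freedom. Power is 91% whatever D is. With three types (two terms), λ × (1 − 2/39) = 16.01 with 34 degrees of freedom gives 90%.

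**Step 4, sensitivity to the mix.** At D = 30, a 20% share gives v = 1.16 and power 87%; a 10% share gives v = 1.09 and power 89%.

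**Step 5, chance imbalance.** With a 50:50 mix and 10 per arm, the highest and lowest arms differ by at least 3 patients of one type in about 67% of simulated allocations.

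**The case against.** The strongest reply is that the documents show no anesthesia mix. The surgeon's block goes to every arm, and the question about anesthesia preference is followed at once by its evident use, screening out patients who want only a block by anesthesia. If anesthesia is in fact uniform, nothing is lost. This stands, and it is why the point is conditional. The plan does not require uniformity either, and it leaves more than one type possible.

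Second, 50:50 is the worst case, and the loss at 30 minutes shrinks with a more uneven split (step 4). This also stands.

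Third, if 30 minutes is the total SD of a mixed cohort, inflating it again counts the mix twice. That is fair as to the starting point: arm-only power would then be 92%. Adjustment would still gain. With D = 30 and p = 0.5, the within-type variance is 900 − 0.25 × 900 = 675, λ = 7.5 × 2025/675 = 22.5, or 21.92 after the factor 38/39, and power is 97%.

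Fourth, the endpoint is secondary, has no stated power, and the unadjusted test is valid. All true. The change is a gain in precision, not the repair of an invalid test.

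A reader might also infer that patients treated under local block alone skip PACU, score 0 minutes and so wreck the endpoint. The documents do not support that. Section 7.1.1 has the patient evaluated in PACU without exception, and no section proposes scoring an absent stay as 0. The only missing-data rule, in section 10.1.2, is written around the diaries and points to removal. Under removal, with the same assumptions, 5-10% of patients without a stay would cost about 2-4 points of power (92% to 90-88%). What remains is a missing sentence on how an absent stay is handled.

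**Conclusion.** The point holds conditionally. The PACU comparison has no anesthesia term, anesthesia beyond the local block is not standardized, and allocation is unstratified. If type varies, the test keeps its validity but loses precision. Under the assumptions above with a 50:50 mix, the arm-only analysis gives up about 6-7 points of power against the adjusted one at a 30-minute difference and about 27-29 points at 60 minutes. At 15 minutes or less the loss is small, and with uniform anesthesia there is none. The SD, the effect, the mix and the difference between types are all assumed, so these figures show a range and do not predict this trial.

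**What to change.** 1. Record planned anesthesia type (general, sedation, local only) before the envelope is opened, using the history already taken under section 7.1.1.
2. In section 10.1.2 and the Protocol Summary, replace the one-way ANOVA with an ANCOVA of PACU time on arm plus planned anesthesia type, with Tukey-Kramer comparisons of the adjusted means. Use the planned type even if the type given later differs, because only the plan is fixed before allocation.
3. As a minor clarification, state that an absent PACU stay is not scored as 0 minutes and is listed by arm. Any restriction of the PACU analysis set must rest on planned anesthesia type alone. Whether a stay occurred is known only after treatment and could depend on it.

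The cost is one data field, a short change to the analysis text and 1-2 degrees of freedom. If anesthesia type has no effect, that is about 1 point of power with two types and nearer 2 with three (92% to 91% or 90%).

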8.3 Time Period and Frequency for Event Assessment and Follow-Up

The occurrence of an AE or SAE may come to the attention of study personnel during study visits and interviews of a study participant presenting for medical care, or upon review by a study monitor. All AEs including local and systemic reactions not meeting the criteria for SAEs will be captured on the appropriate RF. Information to be collected includes event description, time of onset, clinician's assessment of severity, relationship to study product (assessed only by those with the training and authority to make a diagnosis), and time of resolution/stabilization of the event. All AEs occurring while on study must be documented appropriately regardless of relationship. All AEs will be followed to adequate resolution.

Any medical condition that is present at the time that the participant is screened will be considered as baseline and not reported as an AE. However, if the study participant's condition deteriorates at any time during the study, it will be recorded as an AE. UPs will be recorded in the data collection system throughout the study.

Changes in the severity of an AE will be documented to allow an assessment of the duration of the event at each level of severity to be performed. AEs characterized as intermittent require documentation of onset and duration of each episode.

The PI will record all reportable events with start dates occurring any time after informed consent is obtained until 7 (for non-serious AEs) or 30 days (for SAEs) after the last day of study participation. At each study visit, the investigator will inquire about the occurrence of AE/SAEs since the last visit. Events will be followed for outcome information until resolution or stabilization.

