8.6 Safety Oversight

It is the responsibility of the Principal Investigator to oversee the safety of the study. This safety monitoring will include careful assessment and appropriate reporting of adverse events as noted above. Medical monitoring will include a regular assessment of the number and type of serious adverse events.

Data Safety Monitoring

The PI is responsible for conducting systematic and periodic reviews of aggregate data and adverse events in accordance with the data safety monitoring plan. In addition to reviewing AEs, the PI will review assessments of drain site, pain scores, and opioid usage in order to ensure safety of enrolled subjects.

The PI will review all study data and adverse events throughout the study on an annual basis. Administration of study agents will be halted and the study will be discontinued if the PI determines that 3 unexpected and related (possibly related, probably related, or definitely related) AEs have occurred.

A summary of the outcomes of these safety reviews along with accumulated adverse events and deviations will be submitted to the IRB as part of an annual progress report at the time of the Continuing Review submission.

9 Clinical Monitoring

Clinical site monitoring is conducted to ensure that the rights and well-being of human subjects are protected, that the reported trial data are accurate, complete, and verifiable, and that the conduct of the trial is in compliance with the currently approved protocol/amendment(s), with GCP, and with applicable regulatory requirement(s).

CONFIDENTIAL

This material is the property of the NYU School of Medicine and Langone Medical Center. Do not disclose or use except as authorized in writing by the study sponsor
Interventional Template Version: 11 January 2019

Individual subject monitoring for this study will be performed by the PI in an ongoing basis as patients are undergo routine clinical follow-up assessments of their drain sites. We review these clinical assessments and add them to our study data. There are no additional assessments of safety that the patient will need to undergo as part of this study.

10 Statistical Considerations

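### The daily phone call has no adverse-event question, so an event on day 1 after surgery may not be asked about for 2 to 13 days

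*Combined protocol and SAP*

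**What the plan says.** The daily call is described in three places, always with the same task. Section 7.1.1 says "The patients will be called on each day by the study team to ensure that they have been logging their daily pain score" and adds "The study team will call the patient for this purpose". Section 7.2 has participants "called via phone each day by the study team to ensure they have completed their daily log", meaning the pain rating and pill count. Section 10.1.2 says "Patients will be called daily to ensure completion of daily log books". None of the three has the caller ask about symptoms or medical care.

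Adverse-event inquiry is in section 8.3: "At each study visit, the investigator will inquire about the occurrence of AE/SAEs since the last visit". The same section says events may also come to light "during study visits and interviews of a study participant presenting for medical care, or upon review by a study monitor". Section 9 adds no safety assessments beyond routine follow-up.

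Section 7.2 puts the first postoperative visit between days 3 and 14; section 7.1.1 puts it at about 1 to 2 weeks. Sections 8.4.1 and 8.4.2 require events that are both unexpected and at least possibly related to go to the IRB within 48 hours of the study team learning of them. Section 8.5 stops the study once the PI determines that three such events have occurred.

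**The concern.** The study agents are applied once, just before the skin is closed, so the first days after surgery are a natural period in which to look for reactions. In those days the plan puts staff in touch with each participant every day but does not ask them to inquire about harm. The planned question waits for the first visit.

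Two things are at stake. First, mild and short-lived events have to be recalled days later and can be under-recorded. Second, the 48-hour report and the three-event halting rule both depend on the team knowing about an event. The reporting clock starts at awareness, so late awareness delays the report without any breach of the protocol. The halting count can lag behind events in the same way while further participants are treated.

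**Working it through.** The plan states no figure on this point, so there is none to reproduce. The check is a day count on its own visit windows, followed by an accrual calculation.

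**Inputs**
- First postoperative visit: days 3 to 14 (section 7.2), or about days 7 to 14 (section 7.1.1).
- Calls: daily. I count them from day 1.
- Sample size and recruitment: 40 participants in about 2 to 3 months (section 5.4).
- Baseline visit to surgery: up to 3 months (sections 5.5 and 7.2).

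**Wait for the first planned question, event on day 1** (visit day minus 1)
- Section 7.2 window: 3 − 1 = 2 days to 14 − 1 = 13 days.
- Section 7.1.1 window: 7 − 1 = 6 days to 14 − 1 = 13 days.

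**Calls made before that visit** (day 1 to the day before it)
- Visit on day 3: 2 calls. Day 7: 6 calls. Day 14: 13 calls.
- Over the whole diary period, about 14 × 40 = 560 calls are already planned.

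**Further participants treated during the lag**

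Formula: 40 / (months × 30.4 days) × lag in days. A 14-day or 3-day lag is that of an event on the day of surgery first asked about on day 14 or day 3. If surgeries keep pace with enrolment, treatment spans 2 to 3 months. If they trail it by the full 3 months allowed, it could spread over 2 + 3 = 5 to 3 + 3 = 6 months.

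| Treatment spread over | Per day | 3-day lag | 14-day lag |
|---|---|---|---|
| 2 months | 40/60.8 = 0.658 | 2.0 | 9.2 |
| 3 months | 40/91.2 = 0.439 | 1.3 | 6.1 |
| 5 months | 40/152.0 = 0.263 | 0.8 | 3.7 |
| 6 months | 40/182.4 = 0.219 | 0.7 | 3.1 |

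So about 1 to 2 further participants are treated in a 3-day lag and about 3 to 9 in a 14-day lag. These counts cover all four arms. With 10 per arm, about half would be in the two antifibrinolytic arms: 3.1/2 to 9.2/2, or roughly 1.5 to 4.6 in a 14-day lag.

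**With the question added to the call**, the longest gap between planned inquiries up to day 14 falls to about 1 day, with no extra contact.

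**The case against.** The strongest reply is that section 7.2 lists the calls under a heading about intermediate visits, so the visit inquiry in section 8.3 might already cover them. This does not settle the matter. The same list names the in-person visit separately, the calls are made by the study team for a stated purpose, and section 8.3 gives the inquiry to the investigator. If calls are meant to count, the protocol should say so.

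Other routes to detection do exist, and this part of the objection stands. Section 8.3 covers participants presenting for care and monitor review, the PACU stay follows application directly, the first visit may be as early as day 3, and a participant may volunteer a problem on a call. Late discovery is therefore possible, not certain. These routes are more likely to catch severe events than mild ones.

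Three stronger readings are tempting, and the documents do not support them.
- A reader might infer that the PI's safety review in section 8.6 cannot be done in time. That section says "the PI will review assessments of drain site, pain scores, and opioid usage in order to ensure safety of enrolled subjects", while section 7.2 says "Log books will be collected only after postoperative day 14". But section 8.6 sets the review of study data as annual, and diaries returned after day 14 or at 4 to 6 weeks arrive before an annual review. Collection after day 14 also does not bar staff from looking at a diary sooner, although no step plans it.
- A reader might infer that missed nausea, giddiness or pruritus would delay the halting rule. Section 2.4.1 lists these as known risks, so under section 8.2.3 they would ordinarily be expected events and would enter neither the 48-hour report nor the halting count. For them the issue is under-recording only.
- A reader might infer that the trial's safety claim is undermined. Safety is not among the stated objectives or endpoints, and 10 participants per arm could not carry such a claim.

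**Conclusion.** The point holds as a gap in how adverse events are sought. All three descriptions of the daily call confine it to diary completion, and active inquiry is specified only at visits. An event on day 1 may go unasked for 2 to 13 days. Short-lived events can be under-recorded. An unexpected, related event can reach the 48-hour report and the halting count late unless the participant volunteers it or presents for care, or it is seen in the PACU.

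The size is about 3 to 9 further participants treated in a 14-day lag and about 1 to 2 in a 3-day lag, across all four arms. This rests on an even pace of surgery over 2 to 6 months, which the documents do not state. The upper end requires surgeries to keep pace with the fastest expected enrolment. The conclusion itself does not depend on the count.

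**What to change.** In sections 7.1.1, 7.2 and 8.3, state that each existing daily call includes one standard question about new symptoms or medical care, worded identically for all arms. Record the answer on an AE form, and pass any positive answer to the investigator the same day for AE assessment. Reconcile the two statements of the first-visit window in sections 7.1.1 and 7.2.

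Keep the patient diary as the only source for pain scores and pill counts. Taking them by telephone as well would create a second source for the primary endpoint, with no rule for disagreement, in a single-blinded trial with a subjective outcome.

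The cost is a line in the call script, a short form and about a minute more per call. More minor events will be recorded, because a solicited question finds more than a passive one. The fixed, arm-neutral wording is meant to keep that increase similar across arms.
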